## 5.2 Subject disposition

See mock TFLs.

## 5.3 Primary endpoint analysis

Refer to SAP for PACO.

## 5.4 Secondary endpoint analysis

Refer to SAP for PACO.

## **5.5 Exploratory efficacy endpoints analysis**

### **5.5.1 Bleed-related assessments**

The assessments related to bleeding episodes are defined in section [6.2](#).

The definition of bleeding rate, treated bleeds and re-bleeds are defined in the section [5.1](#) of this document and in section 10.3 of protocol version 7. The definition of a target joint is given in the protocol section 9.1.4.

ABR will be calculated at an individual basis as

$$ABR = \left( \frac{\text{Number of treated spontaneous or traumatic bleeds}}{\text{Number of days in the analysis data set}} \right) \times 365.25$$

The continuous/categorical assessments will be presented using descriptive statistics as described in section [5.1](#). The descriptive statistics for the bleed related assessments up until week 56 will be presented by treatment arms and ‘Total concizumab’. Furthermore, it will be presented by haemophilia types (HAwI, HBwI).

The evaluation of bleeding episodes at target joints up until 56 weeks will be done between treatment arms and as ‘Total concizumab’.

These descriptive statistics tables will enumerate results for treated bleeds, zero treated bleeds, cause of bleeds (Spontaneous, Traumatic, Surgical), anatomical location of bleeds (Target joints, Joints, Muscular, Skin, Gastrointestinal, Mouth-gums-nose, Urinary system, Central nervous system, Other), classification of bleeds (Mild/moderate, Severe) and location of severe bleeds (Target joints, Joints, Muscular, Skin, Gastrointestinal, Mouth-gums-nose, Urinary system, Central nervous system, Other). The analysis data set use for these descriptive statistics are mentioned in section [5.1](#) of this document.

### **5.5.2 Pharmacokinetic and pharmacodynamic assessments**

The assessments related to PK and PD are defined in section [6.2](#).

Concizumab concentrations collected during the trial will be used to derive the pharmacokinetic endpoints and assessments based on non-compartmental methods.

All PK and PD endpoints and assessments are continuous and will be presented using the descriptive statistics and analysis sets as described under section [5.1](#).

## **5.6 Exploratory safety analyses**

### **5.6.1 Extent of exposure**

A summary showing subjects that escalate, deescalate, or remain on the 0.20 mg/kg/day dose will be presented by arm.

The length of the periods constituting the analysis data sets and the number of doses taken will be presented descriptively. The output will differentiate between before the pause, after the pause and in total.

### **5.6.2 Adverse events**

All exploratory safety endpoints are defined in section [6.2](#).

All adverse events will be coded using the current version of MedDRA. Hypersensitivity reactions, medication errors and injection site reactions are categorised in the CRF as AEs requiring additional data collection. Additional information on these events will be collected using separate forms. Further, a MedDRA search will also be used to define these events. Thromboembolic events are defined and categorised as AESIs.

Adverse events will be evaluated using descriptive statistics based on the analysis data sets as described in section [5.1](#). These descriptive statistics tables will also be presented by treatment arms and 'Total concizumab'.

Furthermore, for the on-treatment analysis data set the outputs on adverse events will also include information on

- System organ class
- Severity (mild/moderate/severe), seriousness (serious/non-serious) and relation to treatment (possibly/probably/unlikely)
- Adverse events leading to drug discontinuation
- Most frequent adverse events (occurring in more or equal to 5% of subjects)
- Deaths
- Medication errors

The outputs may differentiate between the initial part of the trial and the part after the restart of the trial if deemed relevant.

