## 8 Discontinuation/Withdrawal criteria

### 8.1 Discontinuation of trial treatment

The patient may be discontinued from trial product at any time during the trial at the discretion of the investigator for safety, behavioural, compliance or administrative reasons.

Efforts must be made so that patients, who discontinue trial product, attend and complete all scheduled visit procedures according to the flowchart in Section 2. Patients should stay in the trial irrespective of lack of adherence to the treatment, lack of adherence to visit schedule or missing assessments. Only patients who withdraw consent will be considered as withdrawn from the trial. Patients must be educated about the continued scientific importance of their data, even if they discontinue trial product.

The patient must be discontinued from trial product, if the following applies:

1. Included in the trial in violation of the inclusion and/or exclusion criteria
2. Simultaneous participation in another clinical trial of an approved or non-approved investigational medicinal product
3. Incapacity or unwillingness to follow the trial procedures
4. Significant thromboembolic eventa
5. Event of Disseminated Intravascular Coagulation (DIC)
6. Event of Thrombotic Microangiopathy (TMA)
7. Event of severe or serious hypersensitivity reaction related to concizumab

aThe definition of a significant thromboembolic events is provided in [Appendix 5](#). For venous thromboembolic events where treatment of concizumab has been discontinued, re-initiation of concizumab can be considered by the investigator in the extension part of the trial, after the patient has fully recovered. The investigator must contact and agree with Novo Nordisk before reinitiating concizumab treatment.

See the flowchart in Section 2 for data to be collected at the time of treatment discontinuation and follow-up and for further evaluations that need to be completed.

The primary reason for discontinuation of trial product must be specified in the end-of-treatment-form in the eCRF, and final drug accountability must be performed. A treatment discontinuation session must be made in the IWRS.

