### 9.3.1 Time period and frequency for collecting AE and SAE information

All AEs will be collected from the first trial-related activity after obtaining informed consent and until end of trial visit, at the time points specified in the flowchart.

[figure not shown]
All SAEs will be recorded and reported to Novo Nordisk or designee within 24 hours, as indicated in [Appendix 5](#) for the IMP and on demand treatment, and in [Appendix 8](#) for the investigational medical device. The investigator must submit any updated SAE data to Novo Nordisk within 24 hours of it being available.

Investigators are not obligated to actively seek for AE or SAE in former trial patients. However, if the investigator learns of any SAE, including a death, at any time after a patient has been discontinued from/completed the trial, and the investigator considers the event to be possibly/probably related to the investigational trial product or trial participation, the investigator must promptly notify Novo Nordisk.

The method of recording, evaluating and assessing causality of AE and SAE and the procedures for completing and transmitting SAE reports are provided in [Appendix 5](#) for the IMP and on demand treatment, and in [Appendix 8](#) for the investigational medical device.

Timelines for reporting of AEs, including AESIs are listed in [Figure 4](#).

Some AEs require additional data collection via a specific event form. This includes medication errors observed during the trial. The relevant specific events are listed in [Table 13](#) and the reporting timelines in [Figure 4](#).

**Figure 4** Decision tree for determining the event type and the respective forms to complete with associated timelines

**Table 13** AEs requiring additional data collection (via specific event form) and AESIsa

| Event type                | AE requiring additional event form | AESI |
|---------------------------|------------------------------------|------|
| Thromboembolic events     |                                    | X    |
| Hypersensitivity reaction | X                                  |      |
| Injection site reaction   | X                                  |      |
| Medication error          | X                                  |      |

aRefer to Section [9.3.6](#) for reporting details

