## 4 Analysis sets

For the purposes of analysis, the following analysis sets are defined for the week 56 cut-off.

Subject Analysis Set	Description
Full Analysis Set (FAS)	All subjects randomised to concizumab PPX or on-demand treatment or allocated to arms 3 or 4. Subjects from arms 1 and 2 will contribute to the evaluation ‘as randomised’.
Safety Analysis Set (SAS)	All subjects exposed to concizumab PPX or randomised to on-demand treatment. All subjects will contribute to the evaluation ‘as treated’.

Defined Analysis Data Sets	Description
On-treatment	
The time period where subjects are considered to be affected by on-demand treatment or concizumab treatment.
 
For safety endpoints/assessments relating to events (number of thromboembolic events, number of hypersensitivity type reactions, number of injection site reactions, number of patients with antibodies to concizumab, number of adverse events) the ‘on-treatment’ analysis data set is defined as follows.
 
For subjects in arm 1 during on-demand treatment, the period begins on the date of randomisation (as registered in IWRS) and ends at the first occurrence of:
 

1. Time of permanently ending on-demand administration and initiation of any PPX regimen

2. The last direct subject-site contact, at or prior to the 56 weeks cut-off

3. Withdrawal date for subjects who withdraw informed consent

4. The last subject-investigator/site contact as defined by investigator for subjects who are completely lost to follow up

5. Date of death for subjects

 
For subjects in arm 1 during concizumab PPX treatment, the period begins at the time of initiation of concizumab PPX treatment and ends at the first occurrence of:
 

6. Date of last dose of concizumab + 7 weeks

7. Items 2., 3., 4. or 5. above

 
For subjects in arms 2-4 that start on the new concizumab dosing regimen and who have not been exposed to the initial dosing regimen, the period begins at the time of start of the new concizumab PPX regimen.

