	
For subjects in arms 2-4 that are only exposed to the initial concizumab dosing regimen, the period begins at the time of start of the initial concizumab PPX regimen.
 
For subjects in arms 2-4 that start on the new concizumab dosing regimen and who have been exposed to the initial dosing regimen, the period consists of two periods with a pause in between. The first period begins at the time of start of the initial concizumab PPX regimen and ends 7 weeks after the treatment was paused while the second period begins at the time of start of the new concizumab PPX regimen.
 
For all cases of arms 2-4 above the periods end at the first occurrence of:
 

• Items 2., 3., 4., 5. or 6. above

On-treatment without data on initial regimen	
The time period where subjects are considered to be affected by on-demand treatment or treatment with the new concizumab dosing regimen.
 
The analysis data set is defined similarly as the ‘on-treatment’ analysis data set with the exception:
 

• Observation time during the initial concizumab PPX regimen is excluded

On-treatment without ancillary therapy a excl. data on initial regimen for subjects exposed to both regimens	
The time period where subjects are treated by either the new concizumab dosing regimen or the initial concizumab dosing regimen (only included if not exposed to the new concizumab dosing regimen) or are treated by on-demand treatment and additionally have not used factor-containing products not related to treatment of a bleed during any of the cases.
 
The analysis data set is defined similarly as the ‘on-treatment’ analysis data set with the exception:
 

• Periods where factor containing products not related to treatment of a bleed have been used are excluded

• For subjects in arms 2-4 that start on the new concizumab dosing regimen and who have been exposed to the initial dosing regimen, the data on the initial concizumab PPX regimen are excluded

a Ancillary therapy is defined as use of factor-containing products not related to treatment of a bleed.

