**Table 1 Analysis sets used for analyses and/or presentations of endpoints/assessments**

Endpoint/assessment categories a	Subject Analysis Set	Analysis Data Sets
Bleeding episodes	FAS	On-treatment without ancillary therapy excl. data on initial regimen for subjects exposed to both regimens
PK, PD and safety not relating to events	SAS	On-treatment without data on initial regimen
Safety relating to events b	SAS	On-treatment and On-treatment without data on initial regimen

aWhich endpoints/assessments that belong under each category can be found in section 9 of the protocol version 7.

bThis specifically refers to: number of thromboembolic events, number of hypersensitivity type reactions, number of injection site reactions, number of patients with antibodies to concizumab, and number of adverse events.

For arms 2-4 the target joints registered at baseline will be used for the assessment done at week 56. For arm 1 the target joint evaluation done at visit V9a will be used for assessment at week 56.

Continuous endpoints/assessments will be presented using descriptive statistics which will include min, max, mean, SD, median, and quartiles. For PK endpoints/assessments, the descriptive statistics will also include geometric mean and geometric CV. Event data (including AEs) will be summarised including number of subjects with an event/episode, percentage of subjects with an event/episode, number of events/episodes and rate of events/episodes. Categorical assessments will be summarised by number and percent of subjects in each category. Presentations of results will be by arm and visit (when applicable) and when relevant arm 1 will be split into two parts with on-demand treatment and concizumab treatment.

Baseline for the assessments done at week 56 is defined as the latest non-missing measurement recorded before the time of the first administration of concizumab with the new dosing regimen (arms 2-4 and arm 1 after receiving concizumab) or recorded before randomisation to the on-demand administration (arm 1). If this measurement is missing for arms 2-4 or a subject from arms 2-4 chooses not to restart on concizumab, then the baseline obtained prior to the initial dosing regimen will be used (if available). If the V9a measurement is missing for arm 1 concizumab part,

the latest measurement recorded prior to V9a will be used as a concizumab baseline for arm 1 subjects.

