Assessment	Endogenous thrombin potential (ETP)	At visits where thrombin generation assessments are planned to be measured in the trial up to 56 weeks	nmol/L*min		5.5.2
Assessment	Endogenous thrombin Potential ratio	At visits where thrombin generation assessments are planned to be measured in the trial up to 56 weeks	Ratio		5.5.2
Assessment	Velocity index	At visits where thrombin generation assessments are planned to be measured in the trial up to 56 weeks	nmol/L*min		5.5.2
Assessment	Thrombin lag time	At visits where thrombin generation assessments are planned to be measured in the trial up to 56 weeks	min		5.5.2

Assessment	Time to thrombin peak	At visits where thrombin generation assessments are planned to be measured in the trial up to 56 weeks	min		5.5.2
Assessment	Number of adverse events	On demand (arm 1) • From randomisation to on demand treatment up until start of concizumab treatment	Count	Week 56 cut-off is when all patients from arm 2-4 have completed visit 13a assessments or permanently discontinued treatment.	5.6.2
Assessment	Number of thromboembolic events	Concizumab (arm 1) • From start of the new concizumab dosing regimen up until week 56 cut-off	Count	Concizumab (arm 1) data available up until week 56 cut-off will be presented.	5.6.2
Assessment	Number of hypersensitivity type reactions	Concizumab (arms 2-4) • Before the pause: From start of concizumab treatment (week 0) up until 7 weeks after the treatment pause  as well as  • After the pause: From start of the new concizumab treatment (week 0) up until week 56 cut-off	Count		5.6.2
Assessment	Number of injection site reactions				5.6.2

Assessment	Number of patients with antibodies to concizumab	Concizumab (arms 2-4) 
 
From start of the new concizumab dosing regimen (week 0) up until week 56 cut-off
 
	Count	
Week 56 cut-off is when all patients from arm 2-4 have completed visit 13a assessments or permanently discontinued treatment.
	5.6.3

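### Deaths, SAEs and thromboembolic events more than 7 weeks after the last concizumab dose are collected but assigned to no output that the week-56 SAP specifies

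*SAP*

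**What the plan says.** **Which data sets are used.** SAP 5.1 makes Table 1 the default for every presentation. For safety relating to events, Table 1 names the SAS with "On-treatment and On-treatment without data on initial regimen". Its footnote b leaves no doubt about the scope: "This specifically refers to: number of thromboembolic events, number of hypersensitivity type reactions, number of injection site reactions", followed by antibodies and adverse events. SAP 5.6.2 then lists deaths, seriousness and events leading to drug discontinuation under the sentence "Furthermore, for the on-treatment analysis data set the outputs on adverse events will also include information on".

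**Where those data sets end.** In SAP section 4, a concizumab period (arm 1 after the switch, and arms 2-4) closes at the earliest of several dates, one of which is "Date of last dose of concizumab + 7 weeks". For patients exposed to both regimens, the first period "ends 7 weeks after the treatment was paused" and the second opens with the new regimen. The on-demand period of arm 1 has no such tail rule.

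**What the appendix says.** SAP Appendix 2 gives the time frame for adverse, thromboembolic, hypersensitivity and injection site events in arms 2-4 in two parts. One runs to 7 weeks after the pause. The other reads "After the pause: From start of the new concizumab treatment (week 0) up until week 56 cut-off", with no limit tied to the last dose.

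**What the protocol collects.** Protocol 8.1: "Patients should stay in the trial irrespective of lack of adherence to the treatment". It treats only withdrawal of consent as withdrawal from the trial. Protocol 9.3.1: "All AEs will be collected from the first trial-related activity after obtaining informed consent and until end of trial visit". Patients who never restarted have their own visit schedule in Appendix 12, with adverse events recorded throughout.

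**The concern.** The follow-up rules and the tabulation rules do not match. The protocol follows patients after they stop drug, while the SAP's event tables stop looking 7 weeks after the last dose. A table of deaths built on the on-treatment set could show none while the trial database holds one, and a further thromboembolic event in a patient already off drug would be absent in the same way.

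This matters more than usual here. Development was paused because of thromboembolic events, and protocol 8.1 requires concizumab to be stopped after a significant thromboembolic event, DIC, TMA, or a severe or serious related hypersensitivity reaction. The patients with most uncovered time therefore include those whose later course a reader of the safety section would want to see.

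**Working it through.** The plan states no figure for this point, so there is none to reproduce. The check is textual, followed by date arithmetic for scale.

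**Step 1: does any specified event output reach beyond the tail?**
- Table 1 allows two data sets for event safety. The second is the first minus time on the initial regimen, so it adds no time off drug.
- The third data set in section 4 is used for bleeding episodes. It too is the on-treatment set with time removed.
- Section 4 defines no data set that runs to the end of participation irrespective of treatment.
- The one whole-trial safety listing the SAP specifies (5.6.3) is for positive antibodies, not for deaths or thromboembolic events.

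So no specified event output reaches beyond the tail.

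**Step 2: would Appendix 2 rescue these events if it governed instead of Table 1?**
- For a patient who stops the new regimen and stays in the trial: yes, for the four event counts, because that time frame runs to the cut-off. This conflicts directly with section 4 and Table 1.
- For deaths as a separate output: no, because Appendix 2 has no row for them and 5.6.2 ties them to the on-treatment set.
- For patients who never restarted, and for the rest of the pause: no. The first part of the time frame stops 7 weeks into the pause, and the second part needs a start on the new regimen.

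**Step 3: size for a patient who stops the new regimen.** The stop week *w* is an assumption; the 7-week tail is from section 4. Uncovered weeks up to week 56 = 56 − (*w* + 7).
- *w* = 8: 56 − 15 = 41 weeks.
- *w* = 24: 56 − 31 = 25 weeks.
- *w* = 49 or later: 0 weeks.

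The gap is longer for patients whose observation runs past week 56 before the common cut-off.

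**Step 4: size for patients who restarted.** Protocol 4.3.2.2 places the pause in March to August 2020 without days. Uncovered weeks = (pause in days − 49) / 7.
- Shortest reading, 31 March to 1 August: (123 − 49) / 7 = 10.6.
- Longest reading, 1 March to 31 August: (183 − 49) / 7 = 19.1.

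The range is therefore about 11 to 19 weeks. A patient who restarted after August 2020 would have more.

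**Step 5: how many patients?** The documents do not say. The nearest figure is in protocol 10.1, where fewer than 17% of the randomised patients are expected to withdraw or stop early: 0.17 × 51 = 8.67, so fewer than 9. That figure includes consent withdrawals, who leave follow-up, and it does not cover arms 3 and 4.

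**The case against.** Several points on the other side stand and limit the claim.

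- **The tail is generous and the index event is caught.** Events within 7 weeks of the last dose are tabulated, and 7 weeks matches the protocol's own safety follow-up. The thromboembolic event or reaction that forces discontinuation will normally occur on drug or in the tail, and events leading to discontinuation are a listed output. A reader might infer that events in patients off drug are lost altogether; the text does not support that. An interruption followed by re-initiation on the new regimen also stays inside the window.
- **The limit during the pause is partly the protocol's.** Protocol 4.3.2.2 ends the pre-pause part of the thromboembolic endpoint 7 weeks after treatment was paused, and the SAP follows it. For that endpoint the gap in the pause is by design. Deaths have no such endpoint definition behind them.
- **Unseen specifications.** SAP section 1 and 5.2 leave table specifications and disposition to mock TFLs that are not among the documents. A reader might conclude that these events appear nowhere at week 56. That cannot be shown; what can be shown is that this SAP does not specify them.
- **Appendix 2 may be read as governing.** SAP 5.6.2 refers to it for definitions, so for events after the pause the position is an unresolved conflict. Table 1 names these events expressly, which favours the narrower reading.
- **The full schedule is the wrong yardstick.** A reader might measure the gap for patients who never restarted against the Appendix 12 schedule to week 167. That would count time after this cut-off, which belongs to the end-of-extension evaluation, and the cut-off date is not in the documents.
- **Consequences are limited.** The week-56 outputs are descriptive and test nothing. Reporting of SAEs within 24 hours, the stopping-rule review and DMC review do not depend on these tables. A reader might infer a gap in data collection or patient protection; there is none.

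**Conclusion.** The point holds for the outputs this SAP specifies. Deaths, SAEs and thromboembolic events are tabulated only on data sets that close 7 weeks after the last concizumab dose, or 7 weeks into the pause for the first period of patients who restarted. Later events are collected but assigned to no specified output, whether they occur in patients who stopped permanently and remain in the trial, in those who never restarted, or during the rest of the pause. After the pause, section 4 and Table 1 also contradict the Appendix 2 time frame.

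The per-patient gaps in the working rest on assumed stop weeks and on pause dates known only to the month. The number of patients or events affected cannot be estimated from the documents. This is a shortfall in descriptive reporting that should be corrected; it does not affect the confirmatory conclusions.

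**What to change.** - Add an in-trial data set to SAP section 4, irrespective of treatment. It should run from randomisation (arms 1 and 2) or first concizumab dose (arms 3 and 4) to the end of participation or the 56-week cut-off, whichever is earlier. Tabulate deaths, SAEs and thromboembolic events on it.
- At minimum, specify a listing of all such events to the cut-off, flagged on or off treatment, with the regimen and days since last dose.
- Reconcile section 4 and Table 1 with Appendix 2, stating which time frame governs the event counts after the pause.
- Keep the on-treatment tables as the main adverse event summaries.

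The cost is SAP wording and one or two extra outputs from data already collected. The downside is that some events unrelated to concizumab will appear, but they will be marked as off treatment.
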